In the setting of the current COVID-19 pandemic, all study staff will wear appropriate PPE (as dictated by Partners-wide official policy) while working and during any conversation with study subjects. In addition, patients will only be approached in their room by a study physician to minimize personal contact, at which time they will discuss the study and obtain informed consent from those patients interested in participation. There will be attention to appropriate social distancing, hand hygiene and minimization of sharing any physical objects (e.g. pen, clipboard etc.) throughout the conversation with prospective study subjects. Should patients be interested in participation, written consent will be accepted.

Patients who are designated to have a C/S delivery after labor due to 'failure to progress' will be approached in a similar manner for consent at the time of decision for C/S. Non-English speaking patients undergoing unscheduled, urgent C/S will not be approached since translators may not be available in a timely fashion to assist with consent.

This study will only be conducted in women. Non-English speaking patients undergoing urgent C/S will not be approached since translators may not be available in a timely fashion to assist with consent. No other vulnerable populations will be specifically targeted, nor will any one group bear a disproportionate share of the burdens or benefits of the research.

A total of 1250 women will be enrolled, and 100 randomized in this study based on the power calculation included below and allowing for patient withdrawal or loss to followup; women will be assessed for eligibility and then randomized to either methylergonovine or carboprost groups with the aim of approximately 50 patients per group.

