Within the first 24 hours after delivery, but no sooner than the time of patient transfer from the labor and delivery floor to the postpartum unit, Between 2-4 hours postpartum and again between 18-24 hours postpartum, a blinded study investigator who is not involved in the subject's clinical care will interview the patient by phone (to avoid physical contact and minimize the risk for COVID-10 transmission) and record the information from the interview on the corresponding '2-4 Hr Interview Guide' or '18-24 Hr Interview Guide'. This will allow them to assess subjective side effects of the study medication such as G.I. upset, dizziness, shortness of breath, palpitations or chest pain. Non-English speaking patients will be interviewed in person with the assistance of an in-person interpreter from BWH Interpreter Services.

Subject randomization, patient MRN and the linked study ID number will be documented on a separate form in the secure electronic database, REDCap database by the unblinded principal investigator. This form will be visible only to the principal investigator. An unblinded study investigator (i.e. the principal investigator, or a research assistant, when one is hired in the future) with access to REDCap will be responsible for collecting and entering all primary and secondary outcomes from the Uterine Tone Score Intraop Data Collection sheet, the 2-4 Hour Interview Guide and the 18-24 Hour Interview Guide and Epic medical records (including side-effects of study medications) into REDCap. Subject randomization will be documented, on a separate form in the database to which only the principal investigator has access, in order to preserve the integrity of the data collection and entry.

The need for blood product administration and quantity of each component given within 24hrs after cesarean section will be recorded. In addition, the investigator will record any additional interventions performed to halt bleeding, such as Bakri balloon placement, B-Lynch sutures, uterine artery embolization or hysterectomy.

Total intravenous fluids given from start to conclusion of the delivery will be recorded. The use of vasopressors, uterotonic agents, anti-emetic agents will be recorded. Length of stay and any postoperative complications occurring during the hospital stay will be documented at the time of hospital discharge.

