## VI. BIOSTATISTICAL ANALYSIS

- a. Specific data variables being collected for the study (e.g., data collection sheets).

Baseline patient characteristics will be collected and documented on data collection sheets. These characteristics will include:

1. patient MRN
2. randomization group
3. age
4. height, weight, BMI
5. gravidity and parity
6. baseline hematocrit and platelet count measured at the time of admission or on the day of delivery

- b. Statistical methods

The balance of patient characteristics between the two groups before intervention will be evaluated using standardized differences. Shapiro-Wilk test will be used to confirm whether the primary endpoint, uterine tone score 10 minutes after drug administration, satisfies the normality assumption. Multiple linear regression will be conducted when normality assumption satisfied. In the case when the normality assumption is not established, log transformation/box-cox transformation of the outcome will be carried out before modeling. For secondary endpoints that are dichotomous, logistic regression will be used to

examine the intervention effect after adjusting for potential confounders. For continuous secondary endpoints, such as intrapartum blood loss, we will evaluate its distribution before performing appropriate modeling. Trial site will be included as a covariate in all models to adjust for the stratification of randomization by hospital.

c. Power analysis (e.g., sample size, evaluable subjects, etc.)

Assuming a common within-group standard deviation in uterine tone score of 1.9 points, a minimum sample size of 41 randomized patients per group would provide 80% power at a two-sided alpha level of 0.05 to detect a 1.2 point difference in mean uterine tone score at 10 minutes post secondary uterotonic administration between groups using a two-sample t-test. A total of 50 patients per group (100 patients total) will need to be randomized to account for protocol violations. Since we currently perform 175 C/S monthly at BWH, and approximately 20 patients undergoing non-emergent C/S receive methergine or hemabate for uterine atony each month, we anticipate needing to enroll 1250 patients in total to be able to randomize 100 patients to receive the study intervention.

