## **VII. RISKS AND DISCOMFORTS**

Adverse reactions to methylergonovine include increased blood pressure, seizure, dizziness and headache, and nausea, vomiting, diarrhea and abdominal pain from uterine contractions. Rare effects include chest pain, myocardial infarction, coronary vasospasm, tachycardia, dyspnea, and hematuria. A large retrospective study of over 2 million parturients found no significantly increased risk of acute coronary syndrome or acute myocardial infarction after receiving methylergonovine. ACOG recommendations nonetheless state that methylergonovine should be avoided in patients with hypertension and cardiovascular disease.

The most common adverse reactions to carboprost include nausea, vomiting, diarrhea, as well as headache, myalgias, increased temperature and flushing. Due to its stimulation of smooth muscle contraction, modest increases in blood pressure may be seen, but these are generally clinically insignificant. Additionally, bronchospasm, abnormal ventilation-perfusion and hypoxia may occur, and may be particularly severe in patients susceptible to these complications. Carboprost is therefore contraindicated in patients with active asthma.

Patients with any contraindication to either of the study drugs will be excluded from participation in the study. Patients with a diagnosis of asthma will be interviewed to confirm if their asthma is active. Any patient who has used a bronchodilator within the past 24 months will be considered to have active asthma and will be excluded. If a patient carries a diagnosis of 'childhood asthma' and/or has not needed a bronchodilator for >24 months, they will be considered eligible to participate in the study. After enrollment, patients will be evaluated for all of the above side effects by a clinical investigator between at time of transfer to the postpartum floor and again between 18 to 24 hours after delivery. The obstetric 6-

week postpartum follow-up record will be reviewed by a clinical investigator to screen for thrombotic events or other side effects.

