## **IX. MONITORING AND QUALITY ASSURANCE**

A physician investigator will be present during the entire consent, enrollment and conduct of the study. Criteria for early termination from the study will be observed. Two definitions of early endpoints will be utilized:

1. Subject decision for withdrawal from participation at any time.
2. Any operative or medical condition changes prior to or during the entire study period deemed unacceptable by the obstetrician, anesthesiologist, or physician investigator.

The principal investigator will review all forms and data with every 5th subject to ensure completeness, accuracy and adherence to the protocol. There will be no data safety monitoring board (DSMB) in this study. In place of a DSMB, the Principal Investigator will take full responsibility for standardized review of recruitment at the above frequency, to ensure adherence to protocol, detection of minor or major adverse events (AE's), and timely reporting of such events to the IRB with halting of the study if necessary (for any AE's).

All AE's, whether or not they are considered related to the study, shall be recorded on the Adverse Experience Form within the Case Report Forms (CRFs). The study investigators will comply with the Food and Drug Administration (FDA) regulations requiring the expedited reporting of any AE that is Serious, Unexpected, and Associated with the use of the study drug. AEs will be reported to the PHRC in accordance with the PHRC Policy on Unanticipated Problems Involving Risks to Subjects or Others, including Adverse Events.

Serious AE's include hemodynamic instability requiring epinephrine or norepinephrine or resulting in loss of consciousness or cardiovascular collapse, allergic or anaphylactic reactions to study solution infused, major respiratory complication during hospital admission, or seizure activity. Should any of these events occur, the Principal Investigator will be contacted immediately, the study code broken, and the case reviewed. Serious AE's that occur higher than the expected native incidence will warrant temporarily halting the study and consultation with the Directors of Obstetric Anesthesia ([name]) and Labor and Delivery ([name]).

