medication (based on subject randomization) from the O.R. omnicell and administer it without revealing to anyone in the O.R. which drug was given. They will document the medication in the subject's Epic record in the usual fashion. Obstetricians and nursing staff are not able to view the Epic anesthesia record in real time, and therefore will not be able to see which medication was given by the anesthesiologist. Every effort will be made to avoid having the physician co-investigator be involved in the patient's care. Occasionally, though, if staffing is limited or there is high clinical acuity in the subject's case (e.g. massive postpartum hemorrhage), the anesthesiologist co-investigator who consented the patient may need to be involved in helping with the patient's intraoperative care. If this is the case, coercion will be avoided since the patient consent will occur first, and the study investigator will only become the patient's physician after the informed consenting process is complete. Patients, obstetricians, study co-investigators and nurses will be blinded to the study group assignment but the anesthesiologist will be unblinded to study randomization and the identity of each drug being given.

At the time of administration of the first study drug, the anesthesiologist will ask the obstetrician to rate the uterine tone on a scale of 0 to 10 (0 being 'no tone', 10 being 'excellent tone'). The anesthesiologist will then set a timer. After administration of the study drug, patients will receive our usual standard of care. At 5 minutes and again at 10 minutes from the onset of timing, the anesthesiologist will once again ask the obstetrician for a rating of uterine tone between 0 and 10. These values will be recorded by the anesthesiologist on the Uterine Tone Score Intraop Data Collection sheet provided in the envelope with the Randomization sheet by the investigator.

If a third uterotonic is desired (after oxytocin and the initial study drug), the patient will receive the alternate drug (methylergonovine or carboprost), prepared by the unblinded anesthesiologist. Any additional measures for postpartum bleeding will be provided in the usual fashion as standard of care.

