All participants will be under the direct care of an obstetric anesthesiologist, obstetrician, and a labor and delivery nurse throughout the course of the study. Standard care will be employed for every patient with the exception of the randomization of the order in which they receive their second-line uterotonic agents. At all times, providers' clinical assessment of the patient will be paramount in guiding decision-making. Providers will have full ability to exercise their best judgement in taking care of the patient. If this results in a decision to deviate from the study protocol, the patient will be cared for according to the providers' discretion. If the practice deviates from the study protocol, the patient will be withdrawn from the study thereafter.

Patients will be monitored carefully by their anesthesia and obstetric providers for any potential side-effects of the medications they receive in the study.

The principal investigator will additionally review all data collection and recruitment on every 5th patient recruited and immediately as needed if a concern arises. At the time of each review point, the principal investigator will review all forms and data entry to ensure completeness, accuracy, and adherence to the protocol. Any concern for adverse events will result in immediate review by the principal investigator with the study being temporarily halted, and the events will be reported to the IRB and the PHRC in accordance with the PHRC Policy on Unanticipated Problems Involving Risks to Subjects or Others, including Adverse Events. The principal investigator will be primarily responsible for deciding if the study needs to be stopped, but this can also be decided by any of the study co-investigators.

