Second-Line Uterotonics in Postpartum Hemorrhage: A Randomized Clinical Trial

NCT: 03584854

April 04, 2018

*Biostatistical Analysis Plan*

An a priori power analysis determined that enrollment of 37 patients per group would provide 80% power at a 2-sided alpha level of 0.05 to detect a 1-point difference, with estimated within-group standard deviation of 1.5, in mean uterine tone at 10 minutes after study drug administration using a two-sample t-test. Randomization of 100 patients was planned to account for protocol violations. Uterine tone at 10 minutes (primary outcome) and 5 minutes (secondary outcome) after study drug administration were compared between groups with adjustment for baseline tone and trial site using the generalized estimating equations (GEE) method with an identity link to account for the correlation between repeated measurements on the same patient. The primary analysis was a complete-case analysis, where 3 patients (3%) missing uterine tone at baseline and/or 10 minutes were excluded from the analysis. A multiple imputation sensitivity analysis was also performed which used the multivariate imputation by chained equations approach to impute missing uterine tone values using observed tone measurements (baseline, 5, and 10 minutes), parturient characteristics (age, race, BMI, parity), infant characteristics (number of fetuses, infant birth weight), trial site, interventions (randomized study drug, administration of second study drug, intraoperative transfusion), and outcomes (intraoperative blood loss, change in hematocrit from baseline to 24 hours post-delivery) to create 10 complete datasets. The primary outcome was compared in each of the 10 imputed datasets, and results combined using Rubin's rule.

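### Patients withdrawn after a protocol deviation are not expressly kept in data collection or in an as-randomised analysis: an open risk, mainly for the complete-case secondary outcomes

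*Protocol*

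**What the plan says.** **Exit after randomisation.** The Protocol Summary (Research Design and Methods, the answer on subject safety that follows the secondary endpoints) lets providers depart from the protocol on clinical judgement, then adds: "If the practice deviates from the study protocol, the patient will be withdrawn from the study thereafter". Protocol section IX gives a second route to early termination: "Any operative or medical condition changes prior to or during the entire study period deemed unacceptable by the obstetrician, anesthesiologist, or physician investigator". On blinding, the Summary states that "the anesthesiologist will be unblinded to study randomization and the identity of each drug being given".

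**Follow-up after the 10-minute score.** Protocol section V schedules interviews at 2–4 and 18–24 hours, records blood products to 24 hours, and continues to discharge: "Length of stay and any postoperative complications occurring during the hospital stay will be documented at the time of hospital discharge". Section VII adds a six-week check, in which the "postpartum follow-up record will be reviewed by a clinical investigator to screen for thrombotic events or other side effects".

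**Analysis.** The SAP's primary analysis is complete-case: "3 patients (3%) missing uterine tone at baseline and/or 10 minutes were excluded from the analysis". Multiple imputation of tone is a sensitivity analysis. Its imputation model lists the randomised drug and, separately, receipt of the second study drug. Secondary outcomes are complete-case, with no sensitivity analysis stated. Binary outcomes are reported as adjusted odds ratios, or as risk differences with Fisher's test if the model does not converge. Continuous outcomes are reported as differences in means or medians, or as ratios of geometric means.

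**What is absent.** No text available says whether data collection continues after withdrawal, and none names an intention-to-treat, as-randomised or per-protocol set. The consent form is listed as an attachment but its pages are not in the text, so a statement on data after withdrawal could be there.

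**The concern.** Randomisation protects the comparison only while everyone randomised is counted. Here a decision taken after randomisation, by clinicians of whom one knows the drug, can take a patient out of the study. The reasons could differ by arm: the Summary gives different cautions and different re-administration intervals for the two drugs. If later outcomes are then missing, a complete-case analysis compares selected subsets of the two arms.

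The outcomes are not equally exposed:

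- **Primary (10-minute tone):** largely protected by its timing, the few reported exclusions and the imputation check.
- **Intraoperative secondary outcomes** (5-minute tone, additional uterotonic, intraoperative blood loss): mostly recorded close to the primary.
- **Symptom interviews:** these need continued participation and are the firmest exposure.
- **24-hour, discharge and six-week chart data:** exposed only if abstraction stops at withdrawal.

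Section IX also covers changes before randomisation. Those exits cannot bias a randomised comparison, so only exits after randomisation matter here.

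**Working it through.** **1. The plan's own sample sizes.** Two-sample t-test, two-sided 0.05, noncentrality = difference / (SD × √(2/n)).

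- Protocol section VI: 1.2 / (1.9 × √(2/41)) = 2.86, power 80.7%. The stated 41 per group reproduces.
- SAP: 1.0 / (1.5 × √(2/37)) = 2.87, power 80.8%. The stated 37 per group reproduces.
- Allowance on the Protocol's inputs: 100 − 82 = 18 patients, or 9 of 50 per group (18%). This is an allowance, not a forecast of withdrawals.

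**2. Loss in one arm only, no true difference.** The documents give no rates, so every rate is an assumption. Let the event rate be 20%, and let q1 and q0 be the probabilities of loss for patients with and without the event. Fix the ratio of their odds at k, and choose q0 so that 0.2 × q1 + 0.8 × q0 equals the share of that arm lost. The observed unadjusted odds ratio is (1 − q1) / (1 − q0).

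Example, 10% lost and k = 5: q1 = 0.25 and q0 = 0.0625. Check: 0.2 × 0.25 + 0.8 × 0.0625 = 0.10. Odds ratio = 0.75 / 0.9375 = 0.80.

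| Share of one arm lost | k = 2 | k = 5 | k = 10 |
|---|---|---|---|
| 3% | 0.975 | 0.935 | 0.906 |
| 5% | 0.959 | 0.894 | 0.847 |
| 10% | 0.921 | 0.800 | 0.712 |
| 18% | 0.864 | 0.671 | 0.536 |

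If event-free patients are lost more often (k = 1/2 to 1/10), the odds ratio is 1.02 to 1.03 at 3% and 1.06 to 1.12 at 10%. The direction is therefore not fixed.

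**3. False-positive rate.** Simulation with 50 per arm, Wald test of the log odds ratio, k = 2 to 10: 4.3% with no loss, 4.3–4.7% at 3% lost, 4.5–7.7% at 10%, 4.6–13.8% at 18%. The change at 3% is negligible.

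**4. The same loss mechanism in both arms.** Assume true risks of 20% and 10%. Each arm's odds are multiplied by the same factor, so the odds ratio stays at (0.20/0.80) / (0.10/0.90) = 2.25. The risk difference does move. With 10% lost over the two arms together:

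- k = 2 (q1 = 0.163, q0 = 0.089): risks 18.7% and 9.3%, difference about 9.4 points instead of 10.
- k = 10 (q1 = 0.362, q0 = 0.054): risks 14.4% and 7.0%, difference about 7.5 points.

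Mean and median differences can shift in the same way. If there is no true difference, identical loss in both arms leaves the risk difference at zero.

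**5. Power if deviating patients are kept.** Suppose, pessimistically, that they contribute no treatment contrast. With the Protocol's inputs and 50 per group, the noncentrality is 1.2 × (1 − share) / 0.38.

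| Deviating share | Diluted difference | Power |
|---|---|---|
| 0% | 1.200 | 88% |
| 3% | 1.164 | 86% |
| 10% | 1.080 | 80% |
| 18% | 0.984 | 73% |

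Excluding such patients equally from both arms would give 84% at 10% (45 per group) and 81% at 18% (41 per group), but without the protection of randomisation. These figures use the unadjusted t-test, not the planned baseline-adjusted model.

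**The case against.** The strongest reply is that the SAP already leans towards analysis as randomised. It records the allocated drug separately from receipt of the second drug, and the only exclusion it reports is for missing tone. Three patients as 3% also fits 100 randomised. This stands as indirect evidence for the primary. It does not name the set, does not cover the secondary outcomes, and the rounded percentage would fit any denominator from 86 to 119.

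The trigger is also narrow. A reader might infer that poor response, or a switch to the other drug, removes a patient. The documents do not support that: the alternate drug and all usual measures are within the protocol.

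Loss of later data is inferred. The withdrawal rule looks forward, so earlier data remain. No passage says that chart abstraction stops, and section IX has all adverse events recorded. This stands, and it is why the interviews are the firm exposure and the chart outcomes only a conditional one.

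The extreme scenario is not credible as a forecast: 18% lost with k = 10 needs about 52% of event patients and 10% of event-free patients lost in one arm, and none in the other. It marks the edge of the range and nothing more.

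Finally, a reader might see a conflict between the reasons given for the sample-size allowance: "allowing for patient withdrawal or loss to followup" in section IV and "A total of 50 patients per group (100 patients total) will need to be randomized to account for protocol violations" in section VI. There is none. Under the Summary's rule a violation leads to withdrawal, so both phrases can describe the same patients.

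**Conclusion.** The point holds as a minor one. The plan states a rule that, followed as written, permits loss after randomisation which a clinician who knows the drug can trigger, and no text available keeps those patients in data collection or in a named as-randomised set. The risk falls mainly on complete-case secondary outcomes.

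A reader might go further and conclude that deviating patients were dropped, that the trial's comparisons are biased, or that the primary result is compromised. The documents support none of these: they give no deviation rate, show no lost secondary data and show no difference between arms.

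Size depends on assumption. At 3% of one arm lost, which is the share reported missing for tone and is only borrowed here for secondary outcomes, the effect is small. At 10% it could matter for an odds ratio if loss is strongly tied to the event and confined to one arm. Equal loss in both arms is harmless for the unadjusted odds ratio, but not in general for risk, mean or median differences when a true effect exists. Confidence is medium, because the consent form is not in the text.

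**What to change.** Leave clinical discretion as it is.

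- **Protocol Summary and section IX:** state that a deviation or early termination after randomisation ends protocol-directed treatment only. Scheduled tone scores, interviews and chart outcomes are still collected unless the patient withdraws consent.
- **SAP:** define the analysis population for primary and secondary outcomes as all randomised patients in their assigned arm, and make any per-protocol set a sensitivity analysis.
- **Reporting:** give deviations and missing secondary data by arm.

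The change is to wording and adds no new type of assessment, though staff would complete the scheduled ones for patients who have deviated. The statistical cost is dilution: negligible if deviations are few, but on the pessimistic assumption in the working, power falls to the 80% target at 10% deviating and below it at 18%. The SAP is written in the past tense, so rewording may come too late to recover data that were not collected. Naming the population and reporting deviations and missing data by arm would still be possible.
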